The aim of the present study is to evaluate whether it is safe with regard to surgical complications to offer early breast cancer patients a possibility to preserve the native breast skin with a minimally invasive procedure at a very critical time in the patient pathway. Thus, more extensive reconstructive procedures may be postponed to a less critical point of time in the woman's life.

The present study will add valuable prospectively collected data, to the DBCG population-based database on reconstructive procedures, morbidity, and final outcomes after reconstruction and PMRT.

The protocol for the current study has been changed as of June 2023 from a randomized controlled trial to a prospective study, due to unexpected low accrual (see below).

It is expected that the delayed-immediate reconstructive procedure will become the new DBCG recommendation for patients operated with mastectomy and who will have PMRT. The decision will be made by the DBCG Surgical and Radiation Therapy Committees when the first results are available. Evaluation of morbidity in the accrued patients will continue for 10 years, and if the results at a later time point are not in harmony with the first results, the recommendation in the DBCG guidelines may be altered. The DBCG Surgical and Radiation Therapy Committees decide that.

Hypothesis

Delayed-immediate breast reconstruction does not increase the risk of complications compared with the conventional delayed reconstruction in patients who are to have post-mastectomy radiation therapy.

Aim

The aim of the present trial is to monitor the occurrence of complications after delayed-immediate breast reconstruction, and compare this with delayed reconstruction in breast cancer patients with post-mastectomy radiation therapy. In addition, patient-reported outcomes will be evaluated postoperatively and compared to preoperative measurements.

STUDY POPULATION

Inclusion criteria

- Woman >18 years who are offered a mastectomy for invasive breast can-

cer pT1-3, pN0-N3, M0 and wish reconstruction. The patient can be included no matter the status of estrogen receptor, progesterone receptor, malignancy grade, and HER2 status.

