The patient can be included irrespective of the type and timing of systemic therapy. This trial accepts that randomized patients participate in other trial protocols testing new systemic therapies, e.g. inhibitors of CDK4 and CDK6 kinase activity like abemaciclib in the Monarch E trial. It is also accepted that the patient is included in trials testing loco-regional therapies, e.g. the SENOMAC trial and the

Skagen Trial 1.

TREATMENT PROTOCOL

The first version of the trial was designed as a randomized trial. The inclusion started 1/1-2020. Due to slow accrual, the steering committee has decided to change the trial per 30/6-2023 to a prospective trial of arm A without randomization. It is expected that a prospective trial design will make it feasible for more departments to participate

Treatment arm A

Delayed-immediate reconstruction:

Primary Surgery: Skin sparing mastectomy (nipple sparing if appropriate) and axillary surgery according to guidelines or protocol. Reconstruction with silicone implant or expander covered by pectoral muscle and mesh or matrix.

Delayed reconstruction: Final reconstruction with any reconstructive procedure – being it autologous or implant-based (one- or two-stage, +/- acellular dermal matrix (ADM)) – is performed 6-12 months after completion of chemotherapy and RT. Any contralateral procedure is allowed when doing the delayed surgery, but not in relation to the initial cancer surgery.

Patients, who will not have the second delayed procedure performed will be included in the analysis of 'intention to treat' group and not excluded from the study.

Treatment arm B

Delayed reconstruction:

Primary surgery: Total mastectomy and axillary surgery according to guidelines or protocol.

Delayed reconstruction: 6-12 months after completion of PMRT: final reconstruction with any reconstructive procedure – being it autologous or implant-based (one-or two-stage, +/- ADM). Any contralateral procedure is allowed at any time point after PMRT has been delivered.

This arm recruited patients between 1/1-2020 and 30/6-2023

Concerning post mastectomy radiation therapy (PMRT)

This issue is described in the new ESTRO consensus guidelines for target volume delineation in implant based reconstruction ²⁶.

In general, the tissue beneath the skin surface of the mammarian region is the clinical target volume in all cases.

Implant-based reconstruction and PMRT

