At the first consultation and in the written information about the trial the patient is informed that we want information from her patient file passed on to the trial regarding tumour characteristics, and also about her recurrence and survival status for 15 years after randomization and on events related to the reconstruction. If she has a recurrence we need data passed on from her patient file regarding when and where the recurrence took place. The tumour characteristics are: tumour histological type, size, lymph node status (how many removed and how many with metastasis and what type of metastasis), malignancy grade/ER/PR/HER2/Ki67 status, Q score, resection margin, and surgical procedure, radiation therapy, and systemic treatment. Also information about serious events like a new cancer, heart disease, lung disease and stroke is passed on from her patient file, because these events may be related to the radiation therapy. If an increased risk of any of these events is associated with one of the radiation therapies on trial, it will influence the decision on what is to be future standard therapy.

The patient will be informed that the consent provides the investigators of the study direct access to obtain the necessary information from medical records to conduct the investigation and follow-up.

OUTCOME

Primary endpoint

Any complication deeming *surgical intervention* necessary (excluding percutaneous drainage and antibiotic treatment for inflammation in cases without need for open drainage) within a period up to 1 year after the final reconstruction:

- Infection
- Hematoma
- Loss of implant/expander
- Necrosis
- Seroma

Secondary endpoints

- Necrosis not requiring surgical intervention
- Infection not requiring surgical intervention but antibiotic treatment
- Herniation at donor-site
- Patient's satisfaction and QoL evaluated by BREAST-Q – appropriate modules.
- Psycho-oncological endpoints evaluated by validated questionnaires:
 - Depression (Becks Depression Inventory, BDI)
 - Fear of cancer recurrence (Concerns About Recurrence

Questionnaire-3, CARQ-3)

- Timely initiation of adjuvant therapy
- Morbidity including lymphedema, capsular contracture and range of motion (ROM) of the shoulder
- Breast photos
- Recurrence
 - Local recurrence
 - Regional recurrence
 - Distant metastasis
 - Disease-specific survival
 - Overall survival
- Death including cause of death

Concerning cancer related endpoints

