Is measured at abduction/flexion with the patient sitting in front of a poster with a circle with degrees 0-180° (Appendix X).

Capsular contracture

Capsular contracture is measured by Bakers Grading (Appendix X)

Objective evaluation will be done at follow-up before and 1 year after first surgery and at year ½,1,2,3,4,5, and 10 after second operation and stored in the DBCG database under RECON follow-up.

Photos

Frontal and side-photos pre-operatively with arms down and arms up, before first surgery, after first surgery but before start of radiation therapy, and at year 1, 2, 3, 4, 5, and 10. At any event new photos are taken.

The photos will be stored in a database established for that purpose at Aarhus University Hospital.

The guidelines for photos is in Appendix XI.

BREAST-Q and QoL-questionnaires

TREATMENT ARM A/Prospective study	PRE-OP	POSTOP	POST-OP	POST-FINAL
Delayed-immediate INSTRUMENT		2 WEEKS	9-15 MO (pre-final recon) ###	RECON $\frac{1}{2}+1+2+3+4+5+10$ YEARS
DBCRT Recon Questionnaire*	X	X	X	X
BREAST Q** Part I_B	X		X	
BREAST Q Recon ** Part II_B		X	X	X
BDI Becks Depression Inventory**	X	X	X	X
CARQ-3 Concerns About Recurrence Questionnaire -3**	X	X	X	X

* Mandatory Questionnaires

**Optional Questionnaires for Danish patients only. Data can be stored in RedCap

If the patient does not undergo a final reconstruction, they will have the same POST-FINAL RECONS-questionnaires as the ones who do and at the same time-points, but will not have the PRE-FINAL RECON-questionnaire.

TREATMENT ARM B Delayed reconstruction INSTRUMENT	PRE-OP	POSTOP 2 WEEKS	POST-OP 9-15 MO (pre-final recon)	POST-FINAL RECON ½+1+2+3+4+5+10 YEARS
DBCG RT Recon Questionnaire*	X	X	X	X
BREAST Q** Part I_A	X			
BREAST Q** Part II_A		X		
BREAST-Q** Part I_B			X	
BREAST-Q** Part II_B				X
BDI Becks Depression Inven- tory**	X	X	X	X
CARQ-3 Concerns About Recurrence Questionnaire -3**	X	X	X	X

* Mandatory Questionnaires

**Optional Questionnaires for Danish patients only. Data can be stored in RedCap

STATISTICAL CONSIDERATIONS

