According to a study from our group,¹¹ the risk of having complications that lead to surgical interventions was 26% in patients undergoing delayed reconstruction. Thus, the success rate according to the primary endpoint is 74%. We expect a somewhat worse outcome in this study, but we will not accept a deterioration of more than 10% point, corresponding to a success rate of at least 64. In order to show that, the randomized study should include 295 patients in each group (power 80%, type 1 error 5 % [one-sided test], drop-out rate at 3 years 10%). There will be continuous inclusion of patients until patient No. 590 has been followed for 12 months. The estimation of the inclusion period is thus estimated to 5 years.

After an inclusion period of three years 55 patients from one center have been randomized, whereas the expected number is 354 patients. Due to the slow accrual rate and only one center randomizing patients the trial was changed for a prospective trial without randomization and only one treatment arm. The steering committee will consider then inclusion after another two years to decide whether to close the trial or continue.

12 month after end of inclusion in the prospective part, the complication rate for the randomized part will be calculated in the two groups, though acknowledging that there will not be sufficient power for a statistical comparison. In addition, the complication rate for all patients included in arm A with delayed-immediate reconstruction, included after randomization or in the prospective arm, will be calculated. It is anticipated that the complication rate will not exceed 26%, as for delayed reconstruction.

With a the sample size of 178, a one sided exact test will have 80% power to reject the null hypothesis of inferiority, in favor of the alternative hypothesis that the test proportion is non-inferior to the pre-specified standard, assuming that the expected actual proportion is 0,74, the non-inferiority proportion is 0,64 and that the test is made at the 2,5% significance level. With additional centres participating it is expected that a sample size of 178 patients will be reached after additional two years of inclusion

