APPENDIX

IIa	DBCG RT RECON Primary endpoints after first surgery
IIb	DBCG RT RECON Primary endpoints after second surgery
III	BDI Becks Depression Inventory
IV	CARQ-3 Concerns About Recurrence Questionnaire-3
V	Breast-Q Part I_A Questionnaire before mastectomy
VI	Breast-Q Part I_B Questionnaire before reconstruction
VII	Breast-Q Part II_A Questionnaire after mastectomy
VIII	Breast-Q Part II-B Questionnaire after reconstruction
IX	DBCG RT RECON Questionnaire (morbidity)
X	DBCG RT RECON Registration form (morbidity and cosmesis)
XI	DBCG RT RECON Manual for clinical photos

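### The arm A complication rate is dated 12 months after the end of inclusion, but the primary endpoint window closes about 21 to 27 months after first surgery; if open windows count as no event, the test against 0.64 favours non-inferiority

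*Protocol*

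**What the plan says.** The Outcome section defines the primary endpoint as any listed complication that needs surgical intervention "within a period up to 1 year after the final reconstruction". The Appendix list has a separate form, "DBCG RT RECON Primary endpoints after second surgery", so events after the second operation are part of the endpoint.

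Under Treatment Protocol, the final reconstruction in arm A "is performed 6-12 months after completion of chemotherapy and RT". The arm A questionnaire table places the visit before it at "9-15 MO (pre-final recon", counted from first surgery.

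Statistical Considerations gives one date, "12 month after end of inclusion in the prospective part", and attaches it to the complication rates of the two randomised groups. The next sentence adds that "the complication rate for all patients included in arm A with delayed-immediate reconstruction, included after randomization or in the prospective arm, will be calculated", with no date of its own. The paragraph after that sets out the single-arm exact test: 178 patients, expected success 0.74, non-inferiority bound 0.64, one-sided 2.5%. The section closes by putting all participants of the prospective study into the analyses.

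On use of the result, the introductory text on the study's aim says of the guideline recommendation: "The decision will be made by the DBCG Surgical and Radiation Therapy Committees when the first results are available".

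**The concern.** The analysis date and the endpoint definition do not fit together. A patient enrolled last has 12 months of follow-up when the rate is calculated. She may be just before or just after her second operation, and she cannot have completed the year that follows it. Nothing in the protocol gives a later date for the arm A rate, limits the test to completed windows, or says how an open window is scored.

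If open windows are scored as no complication, follow-up still to come can only remove events from the numerator while the patients stay in the denominator. The error then runs one way, towards concluding that the risk is below 36%. That conclusion is what the study is designed to support, and it would feed the guideline decision.

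**Working it through.** **The plan's own figure.** The smallest r with P(X ≥ r | n = 178, p = 0.64) ≤ 0.025 is r = 127 successes, that is, at most 51 complications. The exact one-sided error is 0.0233, and the power at 0.74 is 0.815. The stated 80% power for 178 patients is reproduced, and the sample size is not in question.

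**When the window closes.** Taking the pre-final visit as a proxy for the date of the second operation: 9 + 12 = 21 months to 15 + 12 = 27 months after first surgery.

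**Who is complete at the analysis date.** The protocol expects about two more years of inclusion. With uniform accrual over 24 months (assumed), follow-up at the analysis runs from 12 to 12 + 24 = 36 months.
- Complete with a 21-month window: (36 − 21)/24 = 62.5%.
- Complete with a 27-month window: (36 − 27)/24 = 37.5%.
- Incomplete: 178 × 0.375 ≈ 67 to 178 × 0.625 ≈ 111 patients. If about 28 arm A patients from the randomised part count towards the 178 (half of 55, assuming 1:1), it is 150 × 0.375 ≈ 56 to 150 × 0.625 ≈ 94.

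Patients from the randomised part, which closed to inclusion before the prospective part began, would have at least 24 + 12 = 36 months. The date suits them; the difficulty lies with the prospective patients.

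**Effect on the test if open windows count as no event.** Let p = 0.36 be the true full-window rate, p₁ the first-stage risk, and G the average share of second-stage events seen by the analysis date. Then

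observed rate = p₁ + (p − p₁) × G, and one-sided error = P(X ≥ 127 | 178, 1 − observed rate).

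Inputs: p₁ = 17% (irradiated patients, N = 24, in the delayed-immediate series under Risk to the Patient) or 13% (complications with expander removal in the 10-year series in the introduction). Assumptions: all 178 prospective, all have a final reconstruction, dates spread evenly over 9 to 15 months, 24-month uniform accrual. The protocol does not give the timing of second-stage events, so three patterns are shown.

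| Second-stage events | G | Observed rate, p₁ = 17% | Error | Observed rate, p₁ = 13% | Error |
|---|---|---|---|---|---|
| Even over the year | 0.747 | 31.2% | 0.26 | 30.2% | 0.36 |
| Early, mean 3 months | 0.876 | 33.6% | 0.09 | 33.1% | 0.12 |
| Very early, mean 1 month | 0.941 | 34.9% | 0.05 | 34.7% | 0.05 |

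Example for the first row: 0.17 + 0.19 × 0.747 = 0.312.

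Variations:
- With 28 earlier, fully followed patients among the 178, the first two rows become 0.19 and 0.075 (p₁ = 17%) or 0.27 and 0.09 (p₁ = 13%).
- With 48 months of accrual and p₁ = 17%, the complete share at a 24-month window is (60 − 24)/48 = 75%, and the error is 0.09, 0.05 and 0.03 for the three rows.
- With every reconstruction at one date and p₁ = 17%, the error is 0.036 (mean 3 months) to 0.11 (even) at 9 months, and 0.24 to 0.51 at 15 months.
- Over a wider grid (24-month accrual, p₁ from 10% to 25%, reconstruction at 9, 12 or 15 months, even or 3-month-mean timing, with or without 28 earlier patients), the error runs from 0.029 to 0.79.

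**The case against.** **The scoring is not in the protocol.** A reader might infer that the complication rate will certainly be understated. The text does not go that far. It says the rate will be calculated and that all participants are included, but not how an open window is scored. A time-to-event estimate could include everyone without treating open windows as successes, and a statistical analysis plan that is not at hand may provide for this. This stands, and the bias has to be stated as conditional. It does not remove the conflict between the date and the endpoint, which lies within the protocol.

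**The date is not labelled as that of a primary analysis.** Grammatically it belongs to the randomised-part rates, which the protocol concedes are underpowered. The arm A rate follows in the next sentence, and the paragraph on the exact test has no date. Carrying the date over is the natural reading, since no other is given, but it remains a reading.

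**The size is open.** A reader might take an error of 10% to 35%, or more, as the expected consequence. The documents do not support a single range. The timing of second-stage events drives the result and is not stated. Accrual may be slower than two years, given 55 patients randomised against 354 expected. Some patients keep their primary implant, which reduces the number of second-stage events still to come. For these patients the window has no stated end at all, so the complete-window shares above do not apply to them.

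**Later correction is possible.** Morbidity evaluation continues for 10 years and the recommendation may be altered. That limits lasting harm but does not make a test on incomplete endpoints sound.

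**Conclusion.** The timing conflict is real. The only date given for the rates falls 9 to 15 months before the endpoint window closes for the last patients (21 − 12 and 27 − 12). With 24-month uniform accrual, 37.5% to 62.5% of prospective patients who have a final reconstruction would have a complete window.

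The effect on the test is conditional. If all participants enter a crude proportion and open windows count as no event, the direction is certain: the complication rate is understated and non-inferiority is favoured. At a true 36% rate, the one-sided error rises from 0.023 to:
- about 0.03 to 0.05 if second-stage events cluster early, or with slow accrual and a mean of 3 months;
- about 0.08 to 0.36 with 24-month uniform accrual, all patients reconstructed, and events at a mean of 3 months or spread over the year;
- more with late reconstruction or back-loaded accrual.

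These are illustrations under stated assumptions, not estimates for this trial. The case for change rests on the mismatch and its direction, not on any one of these figures.

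**What to change.** Run the test against 0.64 when the last included patient has completed 12 months after final reconstruction or, for patients without one, a prespecified fixed time from first surgery. From the protocol's schedule, 15 + 12 = 27 months would be one illustration. It rests on a questionnaire window rather than a surgery date, so the sponsor should choose the value. Reconcile the endpoint definition, the arm A schedule and the date in Statistical Considerations accordingly, including the end of the window for patients who keep the primary implant.

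Label any report at 12 months after the end of inclusion as interim, with incomplete endpoint follow-up and no test against 0.64.

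Cost: a short change to the text, and a confirmatory read-out about 9 to 15 months later. The sample size stays at 178; with complete windows the test keeps its exact error of 0.0233 and power of 0.815. No visits are added, since follow-up already runs to 10 years.

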During the active RCT it was found that some of the included patients did not wish for the delayed (autologous) reconstruction, but rather kept their primary implant. It therefore seems that the rate of capsular contracture is lower than originally expected, perhaps due to a more gentle radiation therapy in the protocol.

For the prospective study, all participants will be included in the analyses, but stratification for type of final reconstruction will be performed.

ETHICAL CONSIDERATIONS

This trial is being conducted according to the 5th version of the Helsinki Declaration. The trial can only start after the approval of the regional ethical committee for Region Midt.

The risk of complications and failure is increased in breast reconstruction after mastectomy in patients who have RT. This is well known but still more and more patients request and receive such procedures.

Patients participating in the present study will be informed that reconstruction combined with RT doubles the risk of complications no matter which treatment arm they belong to. Presumably, delayed-immediate reconstruction will lead to better results and a higher satisfaction to the patients than will delayed, secondary reconstruction if patients have a uncomplicated trajectory. Therefore, if delayed-immediate reconstruction can be performed without increasing other risks, it could turn out to be preferable, and that is what the present study aims to prove.

At present there is no firm evidence and no consensus on which procedure to preferre, but there is an international trend towards primary reconstruction also in this group of patients, and there is a risk that this approach will be routinely adopted before sufficient evidence is available, for which reason it is crucial to first explore this option through a study.

PUBLICATIONS

The results from this study will be published irrespective them being positive, negative, or inconclusive. After approval of the study from the local scientific committee, the study will be registered on www.clinicaltrials.gov according to current recommendations.

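### 178 is used both as the number tested and as the number to be included, with no allowance for loss, so the stated 80% power falls to about 75–78% if 178 is all of arm A and 3–10% are lost

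*Protocol*

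**What the plan says.** Everything needed stands in the protocol's Statistical Considerations section.

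- **Superseded randomised design.** 295 patients per group, 80% power, one-sided 5%, success rates of 74% and 64%, and a "drop-out rate at 3 years 10" per cent.
- **Current single-arm design.** "With a the sample size of 178, a one sided exact test will have 80% power to reject the null hypothesis of inferiority", given that "the expected actual proportion is 0,74", "the non-inferiority proportion is 0,64" and "the test is made at the 2,5% significance level". No drop-out rate is listed.
- **Recruitment.** With more centres, "it is expected that a sample size of 178 patients will be reached after additional two years of inclusion".
- **Analysis set.** The complication rate is to be calculated for all arm A patients, whether they entered by randomisation or through the prospective part. The section adds: "For the prospective study, all participants will be included in the analyses", stratified by type of final reconstruction.

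Under Outcome, the primary endpoint covers complications needing surgery up to 1 year after the final reconstruction.

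**The concern.** The power statement and the recruitment target use the same number. A power figure applies to patients whose outcome is known, whereas a recruitment target counts patients who enter. The two agree only if nobody is lost.

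The randomised calculation in the same section did not assume that, and the follow-up needed is long. The pre-final questionnaire falls 9–15 months after primary surgery and the endpoint runs up to 12 months beyond the final reconstruction, so the window closes roughly 21–27 months after primary surgery. Patients may withdraw at any time.

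This is the only test in the current design for which power is claimed. The protocol concedes that the randomised comparison will be underpowered, and it expects the results to inform a national recommendation. The power quoted should therefore be the one that the planned inclusion delivers.

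**Working it through.** **Inputs, all from Statistical Considerations:** success proportion under the null p0 = 0.64, expected p1 = 0.74, one-sided level 0.025, n = 178, and a drop-out of 10% at 3 years (stated for the randomised design). The 3% and 5% loss rates are assumptions, used to show the range.

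**Method.** For n evaluable patients, r is the smallest integer with P(X ≥ r | n, 0.64) ≤ 0.025. Power is P(X ≥ r | n, 0.74), with X binomial.

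**1. The plan's own figure.** At n = 178, r = 127, the attained level is 0.0233 and power is 81.5%. The stated 80% is reproduced for 178 evaluable patients.

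**2. Is there a hidden reserve?** Exact power moves in steps as n changes:

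| n evaluable | r | Power |
|---|---|---|
| 175 | 125 | 80.7% |
| 176 | 126 | 79.4% |
| 177 | 127 | 78.0% |
| 178 | 127 | 81.5% |

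Losing one or two patients already takes power below 80%. Between 150 and 178, only 175 and 178 reach it. So 178 is not a smaller number inflated for loss.

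**3. Was the randomised figure inflated?** Comparing 0.74 with 0.64 at one-sided 5% and 80% power needs 264 per group by the usual two-proportion formula. Then 264/0.9 = 293.3, rounded up to 294, against the stated 295. The uninflated 264 does not come near it, so the allowance was built in there and is absent from the single-arm calculation.

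**4. Power with 178 included.** At 10% loss, 178 × 0.9 = 160.2 patients remain:

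- n = 160: r = 115, power 76.1%
- n = 161: r = 116, power 74.6%

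Because of the steps, an average over a binomial number of losses is the fairer summary:

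| Loss | Average exact power, 178 included |
|---|---|
| 3% | 78.4% |
| 5% | 77.3% |
| 10% | 75.3% |

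**5. If 178 means evaluable patients.** At 10% loss, 178/0.9 = 197.8, so 198 must be included. Power is 81.5% if exactly 178 remain, and 79.9% averaged over random losses.

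**6. If 178 excludes the arm A patients already randomised.** 55 patients had been randomised after three years. Equal allocation, an assumption consistent with the planned equal groups, puts about 27 in arm A. The total is then 178 + 27 = 205, and average power at 10% loss is 81.6%.

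**The case against.** **The quoted sentence contains no arithmetic error.** This stands. The fault lies in using 178 for two different quantities.

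**The 10% is borrowed.** It belongs to the abandoned randomised design and to 3 years, whereas the endpoint closes at about two. This also stands. Scaling linearly to two years (an assumption) gives 10% × 2/3 ≈ 6.7% loss and average power of 76.4%. The size of the shortfall is therefore a range, but every rate examined from 3% to 10% misses 80%.

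**Loss may be small.** The endpoint is a surgical event registered on database forms, consent gives access to medical records, and patients who do not receive the allocated treatment are still followed unless they refuse. Those without a second operation stay in the analysis. These are good reasons to expect less than 10% loss. They do not support assuming none, and the protocol does not argue that.

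**178 may not be the analysed total.** If it counts only prospective patients, about 205 would be analysed and the power holds even at 10% loss. The text permits this reading without settling it. Nor is 178 a firm cap, since the steering committee will decide after two more years whether to continue.

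**A stronger reading is tempting but not supported.** A reader might infer from the statement that all participants will be analysed that lost patients would count as complication-free, which would inflate the type I error. At a true 36% complication rate with 10% lost, the error would be 6.8% if half of their events went unseen and 16.1% if all did. No passage says that lost patients are scored this way. The statement follows directly on patients who kept their primary implant, so it concerns those without a second operation. Handling of incomplete follow-up may properly be left to a statistical analysis plan, which is not at hand. These figures are therefore not a finding, and they give no ground for replacing the exact test with a cumulative incidence method.

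**Conclusion.** The point holds as a moderate inconsistency. The protocol gives one number for patients tested and patients included, and drops without comment the loss allowance that its previous calculation made. If 178 is the total of arm A patients included, the stated 80% is not delivered once patients are lost. The shortfall is about 2 to 5 percentage points against 80%, or 3 to 6 points against the attained 81.5%.

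This rests on two assumptions: that 178 is the arm A total, and that loss lies between 3% and 10%. Under the other reading of 178 the stated power is met. The design values, the exact test and its significance level are not in question.

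**What to change.** In Statistical Considerations:

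1. State whether 178 means patients included or patients evaluable for the primary endpoint.
2. State whether it counts the arm A patients already randomised.
3. Give an explicit loss assumption for the single-arm design and restate the power for 178 included: about 75% at the protocol's own 10%, with 77% at 5% and 78% at 3% shown alongside. If 178 means evaluable patients, give the matching inclusion number instead (198 at 10% loss).
4. Keep the exact binomial test as specified.

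The cost is a few sentences in the protocol. No extra patients are needed if the lower power is accepted. Keeping about 80% at 10% loss with 178 as the present total would take 198 − 178 = 20 more. If the 178 come on top of the randomised arm A patients, saying so is enough, together with the loss assumption.
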